16.3.4.3. Treatment Preference

The treatment preference questionnaire is taken at Month 11/12 and withdrawal. The nominal visit identifier will be kept as the analysis visit. Data will be reported separately for Month 11/12 and for withdrawal.

16.3.5. Multiple assessments within an Analysis Window

If after window assignment there are multiple valid assessments of a parameter within the same window, then the following hierarchy will be used to determine the value to be used for summary statistics of observed values:

For data other than health outcome:

- the assessment closest to the window target Study Day (or target Injection Study Day if injection study day is used for assessment window slotting);
- if there are multiple assessments equidistant from the target Study Day or target Injection Study Day, then the mean of these values will be used. For HIV-1 RNA, the geometric mean of the number of copies will be used as opposed to the arithmetic mean. For post-dose ECG, the assessment closest to two-hour post injection will be used.

Health outcome assessments:

- if there are multiple assessments assigned to the same analysis visit, the assessment from the original planned nominal visit will be used for summary statistics.
- if there are multiple assessments assigned to the same analysis visit and none originate from a planned nominal visit (e.g. two unscheduled/withdrawal nominal visits), then
 - a. the assessment closest to the window target Study Day will be used;
 - b. if there are multiple assessments equidistant from the target Study Day, then the earliest assessment will be used.

Assessments not chosen for use in summary statistics by this algorithm will still be included in the associated listings. Also, all applicable assessments, irrespective of proximity to the target study day, will be used when categorizing values across visits, such as ‘maximum grade’ or ‘at any time’, and for any algorithm that has specific rules for which observation to use (e.g., snapshot algorithm or CVF identification, where applicable).

16.4. Appendix 4: Study Phases and Treatment State

16.4.1. Study Phases

Assessments and events will be classified according to the time of occurrence relative to the Treatment Start Date defined in Section 16.6.1.

AEs will be assigned to study phases as defined in Section 16.4.1.1.

Laboratory data (efficacy, safety, and virology), HIV associated/ AIDS-defining conditions, health outcomes assessments, vital signs, and ECGs will be assigned to study phases as defined as in Section 16.4.1.2. For example, assessments/events occurring up to and including start of extension phase IP/LTFU ART will be assigned to the Maintenance Phase.

Assessments/events are assigned to study phases sequentially, starting from the top of each table.

16.4.1.1. Study Phases for AEs

Study Phase	Date range
Screen	Date < Maintenance Treatment Start Date
Maintenance	Q2M Arm (OLI and D2I): For participants continuing into Extension Phase: OLI: Maintenance Treatment Start Date ≤ Date < Date of Nominal Month 14 Injection Visit D2I: Maintenance Treatment Start Date ≤ Date < Date of Nominal Month 13 Injection Visit For participants not continuing into Extension Phase: Maintenance Treatment Start Date ≤ Date < LTFU ART Start Date (if applicable) Note: - For AEs leading to withdrawal and started on the same date as LTFU ART Start Date, Maintenance Phase, instead of Long-term Follow-up phase, will be assigned. - LTFU ART start date is not applicable for those who complete maintenance phase and transition to commercial supply.
	BIK Arm: For participants continuing into Extension Phase: Maintenance Treatment Start Date ≤ Date < min (Start Date of Extension Phase CAB/RPV oral lead-in, Date of first Extension Phase CAB/RPV injection) For participants not continuing into Extension Phase: Date ≥ Maintenance Treatment Start Date

Study Phase	Date range
Extension	
Participants continuing maintenance CAB LA + RPV LA into Extension Phase OLI: Date of Nominal Month 14 Injection Visit ≤ Date < LTFU ART Start Date (if applicable) D2I: Date of Nominal Month 13 Injection Visit ≤ Date < LTFU ART Start Date (if applicable)
 
Participants Switching from Maintenance BIK Arm to CAB LA + RPV LA: min (Start Date of Extension Phase CAB/RPV oral lead-in, Date of first Extension Phase CAB/RPV injection) ≤ Date < LTFU ART Start Date (if applicable)
 
Note: LTFU ART start date is not applicable for those who transition to commercial supply.

 • Date = AE Start date • Maintenance Treatment Start Date: refer to Treatment Start Date in Section 16.6.1 	

16.4.1.2. Study Phases for Lab assessments, ECG, Vital Signs, Health Outcomes, Protocol Deviations, and HIV associated/AIDS-defining conditions

Study Phase	Date range
Screen	Date ≤ Maintenance Treatment Start Date
Maintenance	
Q2M Arm:
 
For participants continuing into Extension Phase: OLI: Maintenance Treatment Start Date < Date ≤ Date of Nominal Month 14 Injection Visit D2I: Maintenance Treatment Start Date < Date ≤ Date of Nominal Month 13 Injection Visit
 
For participants not continuing into Extension Phase: Maintenance Treatment Start Date < Date ≤ LTFU ART Start Date (if applicable)
 
Note: LTFU ART start date is not applicable for those who complete maintenance phase and transition to commercial supply.

Study Phase	Date range
	
BIK Arm: For participants continuing into Extension Phase: Maintenance Treatment Start Date < Date ≤ min (Start Date of Extension Phase CAB/RPV oral lead-in, Date of first Extension Phase CAB/RPV injection)
 
For participants not continuing into Extension Phase: Date > Maintenance Treatment Start Date

Extension	
Participants continuing maintenance CAB LA + RPV LA into Extension Phase OLI: Date of Nominal Month 14 Injection Visit < Date ≤ LTFU ART Start Date (if applicable) D2I: Date of Nominal Month 13 Injection Visit < Date ≤ LTFU ART Start Date (if applicable)
 
Participants Switching from Maintenance BIK arm to CAB LA + RPV LA: min (Start Date of Extension Phase CAB/RPV oral lead-in, Date of first Extension Phase CAB/RPV injection) < Date ≤ LTFU ART Start Date (if applicable)
 
Note: LTFU ART start date is not applicable for those who transition to commercial supply.

- **Date** = start or assessment date
- **Maintenance Treatment Start Date:** refer to Treatment Start Date in Section 16.6.1

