 4. Listing of all AEs including verbatim text and preferred term, and listing of subject numbers for individual AEs.
 5. Common AEs are those with $\geq 5\%$ incidence in Q2M or BIK summarised by frequency.
 6. Plots of incidence rates and relative risk with 95% CI for Q2M vs.BIK.
 7. Four PSRAE listings: Event and Description (Section 1 and Section 2), Possible Cause (Section 3), Section 4 and Section 5 - Section 8.

8. Shift table summarising Maintenance Baseline (Day 1) vs. maximum Maintenance Phase result.
9. Scatter plot of baseline vs. maximum post-baseline for ALT and BILT. Scatter plot of maximum ALT vs. maximum Bilirubin.
10. Bone markers: Bone-specific alkaline phosphatase, procollagen type 1 N-propeptide, type 1 collagen cross-linked C-telopeptide, osteocalcin, 25 hydroxy-Vitamin D. Renal markers: Cystatin C; Beta-2-Microglobulin; Retinol Binding Protein (RBP). CCI
11. For subjects meeting hepatobiliary lab abnormality criteria.
12. Repeat for CAB/RPV, CAB, RPV respectively.
13. Separate listings for exposure to abacavir, history of drug allergies, family conditions, skin rash, symptoms, vital signs, individual symptoms and diagnostic category assignment. If no hypersensitivity to abacavir is observed, then only one blank listing will be provided for the exposure to abacavir.
14. Separate listings for event reporting, RUCAM score, biopsy, imaging, substance use and medical conditions. CCI
16. Statistical analysis will be performed for HOMA-IR.
17. Event-level summary: Percentages based on total number of ISR events including distribution of grade, duration, and event characteristics.
18. Subject-Level summary: Characteristics of ISR AE (Overall and by Common ISRs); Percentage based on number of participants; Includes distribution of grade and max grade, event characteristics, number of events per subject, rate of number of events per injection visit.
19. A corresponding plot for all grades and a separate plot for grade 3-5 events will be produced.
20. Patient profiles are not planned but can be produced post hoc, as necessary.
21. Please refer to Section 5.4 for derivation of needle length used in this summary.
22. For subjects with any value of potential clinical importance.

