16.3.2. Definitions of Assessment Windows for Data Other than Health Outcomes

16.3.2.1. Assessment Windows for Screening, Maintenance and Extension Phase Data – Q2M OLI Subjects

All Parameters except for where noted ^(d)	Analysis Window	Target Study Day	Target Injection Study Day	Analysis Timepoint 1	Analysis Timepoint 2	Notes
	Study Day \leq 1	Study day of the earliest record		Screening	Screening	Screening
	Last available recorded value up to and including the date of first Maintenance Phase dose of IP	1		Maintenance Baseline (Day 1)	Maintenance Baseline (Day 1)	Maintenance Baseline (Day 1)
Post-dose ECG	Value taken post-dose	1		Day 1 (Post Dose)	Day 1(Post Dose)	Day 1(Post Dose)
	Injection Study Day \leq 15 and Study Day \geq 2 For those with OLI only: $2 \leq$ Study Day \leq Study Day of Last Oral Dose + 1	31	1	Month 1	Month 1	Injection 1
Urinalysis	Injection Study Day \leq 42 and Study Day \geq 2 For those with OLI only: $2 \leq$ Study Day \leq Study Day of Last Oral Dose + 1					
Post-dose ECG	Value taken post-dose Month 1					
	$16 \leq$ Injection Study Day \leq 60	61	31	Month 2	Month 2	Injection 2
	$61 \leq$ Injection Study Day \leq 120	121	91	Month 4	Month 3/4	Injection 3
	$121 \leq$ Injection Study Day \leq 180	181	151	Month 6	Month 5/6	Injection 4
Urinalysis ^(d) , CD8, CD4/CD8 ratio, fasting glucose and lipids ^(d) , weight, height, BMI, Waist and Hip Circumference, Vital Signs ^(d) , Insulin, HbA1c, HOMA-IR,	$121 \leq$ Injection Study Day \leq 192					

All Parameters except for where noted ^(a)	Analysis Window	Target Study Day	Target Injection Study Day	Analysis Timepoint 1	Analysis Timepoint 2	Notes
Renal, Bone and CCI						
	$181 \leq \text{Injection Study Day} \leq 240$	241	211	Month 8	Month 7/8	Injection 5
	$241 \leq \text{Injection Study Day} \leq 300$	301	271	Month 10	Month 9/10	Injection 6
	$301 \leq \text{Injection Study Day} \leq 360$					
Urinalysis ^(a) , CD8, CD4/CD8 ratio, fasting glucose and lipids ^(a) , weight, height, BMI, Waist and Hip Circumference, Vital Signs, CCI, Insulin, HbA1c, Renal, Bone and CCI ^(a)	$301 \leq \text{Injection Study Day} \leq 372$	361	331	Month 12	Month 11/12	Injection 7
	$361 \leq \text{Injection Study Day} \leq 420$ For those who did not continue to Extension after completing Maintenance Phase: $361 \leq \text{Injection Study Day} \leq \text{Injection Study Day of: max}(\text{Last Injection Date} + 67, \text{Date of Last Oral Dose} + 1)$	421	391	Month 14	Month 13/14	Injection 8

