Urinalysis ^(a) , CD8, CD4/CD8 ratio, fasting glucose and lipids ^(b) , weight, height, BMI, Waist and Hip Circumference, Vital Signs, CCI , Insulin, HbA1c, Renal, Bone and CCI	$121 \leq \text{Study Day} \leq 192$				
	$181 \leq \text{Study Day} \leq 240$	211	Month 7	Month 7/8	Injection 5
	$241 \leq \text{Study Day} \leq 300$	271	Month 9	Month 9/10	Injection 6
	$301 \leq \text{Study Day} \leq 360$	331	Month 11	Month 11/12	Injection 7
Urinalysis ^(a) , CD8, CD4/CD8 ratio, fasting glucose and lipids ^(b) , weight, height, BMI, Waist and Hip Circumference, Vital Signs, CCI , Insulin, HbA1c, Renal, Bone and CCI	$301 \leq \text{Study Day} \leq 372$				

All Parameters except for where noted ^[d]	Analysis Window	Target Study Day	Analysis Timepoint 1	Analysis Timepoint 2	Notes
	$361 \leq \text{Study Day} \leq 420$ For those who did not continue to Extension after completing Maintenance Phase: $361 \leq \text{Study Day} \leq \max(\text{Last Injection Date} + 67, \text{Date of Last Oral Dose} + 1)$	391	Month 13	Month 13/14	Injection 8
	$(30*m - 29) \leq \text{Study Day} \leq (30*m + 30)$	$30*m + 1$	Month 15, 17, etc.	Month m/m+1	Injection ((m+3)/2)
If subject permanently discontinued study treatment:					
	Date > min(LTFU ART start date, max(Last Injection Date + 67, Date of Last Oral Dose + 1))		Follow-up	Follow-up	Follow-up

NOTES:
 
 • Analysis windows are applied after data has been assigned to the Maintenance Phase and Extension Phase as defined in Section 16.4.1 • Study day is defined in Section 16.6.1 • Follow-up will be derived only for participants who permanently discontinued study treatment. • Last oral dose may be CAB/RPV or SOC ART Oral Bridging where CAB/RPV is not available due to COVID-19 impact. 
[a] Urinalysis: All parameters provided by the central laboratory under the category of urinalysis. [b] Lipids: Cholesterol, HDL Cholesterol Direct, LDL Cholesterol Calculation, LDL Cholesterol Direct, Total Cholesterol/HDL Cholesterol Ratio, Triglycerides [c] Bone Markers: Bone-specific alkaline phosphatase, Procollagen type 1 N-propeptide, Type 1 collagen cross-linked C-telopeptide, Osteocalcin, 25 hydroxy-Vitamin D; Renal Markers: Cystatin C, Retinol Binding Protein, Beta-2-Microglobulin; CCI [d] Analysis windows for parameters with sparse collection are noted.
					

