16.4.3. Treatment State

Within each treatment study phase (i.e. Maintenance, and Extension—based on assignment of study phase described in Section 16.4.1), only those assessments which occur within the ranges shown below will be considered ‘on-treatment’ for the given phase. Note “on-treatment” criteria will not be implemented for adverse event summaries.

Table 7 Treatment State within Study Phases

Study Phase ^a	Treatment State	Date Range
Screen	Pre-treatment	All assessments/events within Phase
Maintenance	On-treatment	Q2M Arm: Date ≤ max (Date of Last Injection Dose + 67, Date of Last Oral Dose + 1)
		BIK Arm: Date ≤ Maintenance ART Stop Date + 1
	Post-treatment	Q2M Arm: Date > max (Date of Last Injection Dose + 67, Date of Last Oral Dose + 1)
		BIK Arm: Date > Maintenance ART Stop Date + 1
Extension	On-treatment	Date ≤ max (Date of Last IP Injection Dose + 67, Date of Last Oral Dose + 1)
	Post-treatment	Date > max (Date of Last IP Injection Dose + 67, Date of Last Oral Dose + 1)
Long-Term Follow-up	On-treatment	Date ≤ min (LTFU ART start date, max (Date of Last IP Injection Date + 67, Date of Last Oral Dose + 1))
	Post-treatment	Date > min (LTFU ART start date, max (Date of Last IP Injection Date + 67, Date of Last Oral Dose + 1))
Note: 
 Treatment State is determined after data has been assigned to the study Phases as defined in Section 16.4.1 		

- The upper bound with last IP injection / last oral dose /Maintenance ART Stop Date should only be applied to participants who permanently discontinue from study treatment
- Date = Assessment/Start Date.
- Last oral dose may be CAB/RPV or SOC ART Oral Bridging where CAB/RPV is not available due to COVID-19.

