16.15.8. Safety Figures

Safety: Figures					
No.	Population	GSK Standard / Example Shell	Title	Programming Notes	Deliverable [Priority]
Adverse Events					
3.1.	Safety	AE10	Plot of Common Maintenance Phase Adverse Events and Relative Risk(Excluding ISRs) – Q2M vs. BIK	207966/primary_15/F3.1	M6, M12
3.2.	Safety	mid201584/primary_07/T3.14	Plot of Incidence of Maintenance Phase Drug-Related Injection Site Reaction Adverse Events by Visit (Overall and Common)	Q2M only. 3 Sections: CAB and or RPV CAB RPV	M6, M12
3.3.	Safety	201584/primary_07/F3.17	Plot of Incidence of Grade 3-5 Maintenance Phase Drug-Related Injection Site Reaction Adverse Events by Visit (Overall and Common)	Q2M only. 3 Sections: CAB and or RPV CAB RPV	M6, M12
Laboratory					
3.4.	Safety	LIVER14	Scatter Plot of Maximum vs. Baseline for ALT and BILT – Maintenance Phase	GSK Statistical Display Standard Q2M and BIK	M6, M12
3.5.	Safety	LIVER9	Scatter Plot of Maximum ALT vs. Maximum Total Bilirubin– Maintenance Phase	GSK Statistical Display Standard Q2M and BIK. Remove the reference lines where ULN = 1X (only keep the 2X for BILT and 3X for ALT).	M6, M12

Safety: Figures					
No.	Population	GSK Standard / Example Shell	Title	Programming Notes	Deliverable [Priority]
3.6.	Safety	mid207966/primary_15/F3.18	Bar Chart of Fasting Lipid NCEP Categories	Baseline, M5/6 and M11/12. Include all 4 parameters: Triglycerides, Total Cholesterol, LDL, HDL	M6, M12
3.7.	Safety	mid215307/iss_01/F3.5	Bar Chart of Total Cholesterol/HDL Ratio Categories	Q2M and BIK . Baseline, M5/6 and M11/12. Keep big N as denominator	M6, M12
3.8.	Safety	mid215307/iss_01/F3.6	Bar Chart of Fasting Blood Glucose	Q2M and BIK . Baseline, M5/6 and M11/12 Keep big N as denominator	M6, M12
3.9.	Safety	207966/primary_15/F3.21	Plot of Incidence of Maintenance Phase Drug-Related Injection Site Reaction Adverse Events by Strata and Visit (Overall and Common) - CAB and/or RPV	Q2M only. Color-code Severity grade within each bar	M6, M12
3.10.	Safety	SAF_F1	Line Plot of Mean Change from Baseline by Visit for Bone, Renal, Inflammation and Insulin Resistance Markers		M12

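### Maintenance Phase AEs are counted over unequal periods by arm for participants who enter the Extension, but compared as crude incidence, which usually tilts the comparison against Q2M

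*SAP*

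**What the plan says.** Section 16.4.1.1 of the SAP assigns AEs to study phases by onset date. For participants who continue into the Extension, the Maintenance Phase is defined as follows:

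- Q2M, OLI: "Maintenance Treatment Start Date ≤ Date < Date of Nominal Month 14 Injection Visit"
- Q2M, D2I: "Maintenance Treatment Start Date ≤ Date < Date of Nominal Month 13 Injection Visit"
- BIK: "Maintenance Treatment Start Date ≤ Date < min (Start Date of Extension Phase CAB/RPV oral lead-in, Date of first Extension Phase CAB/RPV injection"), which is the Month 13 visit

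Participants who do not continue have other limits. Q2M runs to the start of long-term follow-up ART, where that applies. BIK has no upper limit, although these participants complete the study at Month 12 (section 2.3).

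Section 16.3.2 sets target days for the closing visits. The OLI row reads "421 391 Month 14 Month 13/14 Injection 8", where the first figure is the target Study Day. The D2I row reads "391 Month 13 Month 13/14 Injection 8". The BIK table puts Month 13 at Study Day 365, because BIK visits run every 56 days.

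The comparative display is described in section 8.1, Table 3, note 6 as "Plots of incidence rates and relative risk with 95% CI for Q2M vs.BIK". It is listed in section 16.15.8 as Figure 3.1, "Plot of Common Maintenance Phase Adverse Events and Relative Risk(Excluding ISRs"). Note 5 of the same table defines common AEs as those with at least 5% incidence in either arm. SAEs, AEs leading to withdrawal and AESIs are summary tables by arm (section 16.15.7, for example Tables 3.13, 3.17 and 3.71). No person-time denominator or common cut-off day is defined for any of these displays.

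**The concern.** A participant watched for longer has more chance to report an event. If one arm's window is systematically longer, its crude incidence is higher even when the underlying rates are the same, and a relative risk of 1 is no longer the value expected under no difference. Here the longer windows belong to Q2M, so for participants who continue the bias runs against the new regimen.

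The SAP deals with the same calendar mismatch elsewhere. Section 16.3.2.3 adapts the BIK windows to the 56-day schedule, and section 16.3.2.6 gives all three groups Month 11/12 Snapshot windows of equal width. AEs get no comparable treatment. At stake is the between-arm safety reading: the point estimates and intervals in Figure 3.1, and the informal comparison of percentages in the SAE, AESI and withdrawal tables.

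**Working it through.** **1. Reproduce the SAP's target days** (section 16.3.2).

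- OLI Month 14: 30 × 14 + 1 = 421
- D2I Month 13: 30 × 13 + 1 = 391
- BIK Month 13: 6 × 56 + 28 + 1 = 365

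All three match the SAP.

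**2. Window length.** The AE must start before the closing visit, so length = target day − 1: 420 days (OLI), 390 (D2I), 364 (BIK).

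**3. Time ratios to BIK.** OLI: 420/364 = 1.154. D2I: 390/364 = 1.071.

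**4. Expected relative risk with no true difference.** Assume the same constant hazard h in both arms. Let p be the BIK risk over 364 days, so h = −ln(1 − p)/364. Let w be the OLI share of Q2M. It is participant choice and not stated, so it is taken from 0 to 1. Then

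Q2M risk = w[1 − exp(−420h)] + (1 − w)[1 − exp(−390h)], and RR = Q2M risk / p.

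| BIK risk | all D2I | 35% OLI | 50% OLI | all OLI |
|---|---|---|---|---|
| 1% | 1.071 | 1.100 | 1.112 | 1.153 |
| 5% | 1.069 | 1.097 | 1.109 | 1.149 |
| 20% | 1.063 | 1.088 | 1.099 | 1.135 |
| 50% | 1.048 | 1.067 | 1.075 | 1.101 |

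At 5% BIK risk the absolute excess is 0.35 to 0.75 percentage points. An inflation of exactly 10% in time needs w = (1.10 × 364 − 390)/30 = 0.35.

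**5. Non-continuers.** Suppose they stop at the Month 12/11 visit: OLI 360, D2I 330, BIK 336 days (target days 361, 331 and 337, minus 1). The continuing shares are assumptions.

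- 80% continue in both arms. BIK averages 0.8 × 364 + 0.2 × 336 = 358.4 days. All D2I gives 378/358.4 = 1.055; all OLI gives 408/358.4 = 1.138.
- All of Q2M and 80% of BIK continue: 390/358.4 = 1.088 to 420/358.4 = 1.172.
- Half of Q2M (all D2I) and all of BIK continue: 360/364 = 0.989, so the direction reverses.

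**6. Size against precision.** With 654 randomized 2:1, the arms are 436 and 218. At 5% risk in both, SE(log RR) = √[0.95/(0.05 × 436) + 0.95/(0.05 × 218)] = 0.36, so a 95% interval around RR = 1 runs from about 0.49 to 2.03. With the shifts above, the chance that the lower limit exceeds 1 under equal hazards rises from a nominal 2.5% to between 3.8% (all D2I) and 5.9% (all OLI) at 5% BIK risk. At 20% BIK risk it is between 5.6% and 12.0%.

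**7. With a common cut day,** or with events per unit of person-time under the same constant hazard, the expected ratio is 1.00.

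**The case against.** The case for leaving the plan alone has several parts.

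- **The Q2M window has a rationale.** It keeps the full dosing interval after the Month 12 or Month 11 injection. That justifies it as a phase definition, but does not make it a like-for-like comparison period.
- **The day counts are conditional.** They hold only for Extension continuers. Non-continuers dilute the effect, and the open-ended BIK limit for those who stop early pulls the other way. This stands, although it takes about half or more of Q2M not continuing to reverse the direction.
- **The data cut truncates follow-up.** The Month 12 analysis starts once everyone has completed Month 12/11 (section 3.2), so late enrolees will not all have reached Month 13 or 14. This stands for that analysis. It would not reduce the imbalance in the by-phase tables repeated at End of Study.
- **The imbalance is partly visible.** Table 3.1 shows exposure by phase, and Table 3.21 gives cumulative AEs by preferred term and visit. Neither corrects Figure 3.1 or the SAE, AESI and withdrawal tables.
- **The shift is small beside the confidence intervals,** and no AE hypothesis is tested. This stands and limits the priority.

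A reader might go further and infer three things that the SAP does not support. First, that Q2M will look about 10% worse: that figure needs about 35% OLI and a constant hazard, and the SAP fixes neither. Second, that relative risks for SAEs and AESIs are distorted: none are planned, since Figure 3.1 covers only common AEs other than injection site reactions. Third, that the statement in section 16.4.3 that on-treatment "criteria will not be implemented for adverse event summaries" causes the problem: the on-treatment upper bound applies only to participants who permanently discontinue, so it would not shorten any continuer's window.

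In the other direction, the words incidence rates in note 6 might suggest person-time rates, but the SAP defines no such denominator for AEs.

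**Conclusion.** The concern holds in this limited form. For Extension continuers the Maintenance AE windows are about 420, 390 and 364 days, and the planned comparisons make no allowance for it. Under equal, constant hazards the expected ratio for a low-incidence AE is 1.07 (all D2I) to 1.15 (all OLI), falling to 1.05 to 1.10 when the BIK risk is 50%. The result assumes target-day visits, an unknown OLI/D2I split, a constant hazard and continuation into the Extension. Early clustering of AEs, a low Q2M continuation rate or truncation at the data cut would each make it smaller. The bias is modest but systematic, usually against Q2M, and easily removed, so the plan should be changed. It does not invalidate the safety analysis.

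**What to change.** 1. Base Figure 3.1 either on AEs with onset up to one fixed Study Day common to all arms (for example Day 337, the BIK Month 12 target), or on exposure-adjusted rate ratios. The fixed day does not rely on a constant hazard. A rate ratio does, and would over-correct in favour of Q2M if AEs cluster early.
2. Add exposure-adjusted incidence rates beside the crude between-arm AE, SAE, AESI and AE-withdrawal tables, using the overall exposure already derived in section 16.6.4. State that counted events must start within the counted person-time.
3. Keep the full-phase tables and label them descriptive.
4. Do not use the Month 11/12 visit as the common cut. Its target days are 361, 331 and 337, so time would stay unequal: 360/336 = 1.07 for OLI and 330/336 = 0.98 for D2I.

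The cost is SAP wording and a little programming, with no new data. A Day 337 cut leaves later AEs out of the comparative figure, including those after the OLI Month 12 injection, but they remain in the full-phase tables. D2I participants last seen at their Month 11 target (Day 331) fall six days short of the cut, which is negligible.

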5.2. Baseline Definitions

For all endpoints (except as noted in baseline definitions) the baseline value will be the latest pre-dose assessment with a non-missing value, including those from unscheduled

visits. If time is not collected, Day 1 assessments are assumed to be taken prior to first dose and used as baseline.

Electrocardiograms (ECGs) are to be performed in triplicate prior to first dose on Day 1. The baseline value for an ECG parameter will be the mean of the last pre-treatment set of assessments from the same date.

Unless otherwise stated, if baseline data is missing no derivation will be performed and baseline will be set to missing.

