- f. Physical exams should be conducted as part of normal routine clinical care. Medical assessments include any decisions the study staff must make for participants management and/or care of participant.
- g. Height collected at Baseline Day 1 only. Recommended procedures to measure weight, waist and hip circumference can be found in protocol Section 10.10. Weight related measurements to be collected are weight, body fat %, total body water %, muscle mass, and bone mineral mass.
- h. Measure vital signs after about 5 minutes of rest in a semi-supine position.

- i. A 12-lead ECG will be performed after resting in a semi-supine position for at least 5 minutes. ECGs will be performed pre-dose. ECG pre-dose will be performed in triplicate at Day 1. A 2-hour post-dose ECG will also be performed at Day 1 (D2I), Month 1 (OLI) and Month 12 (OLI)/Month 11 (D2I) for participants receiving CAB LA + RPV LA with an allowable window of ± 30 minutes.
- j. Only SAEs related to study participation or to a concomitantly administered Viiv/GSK product will be collected between obtaining informed consent and administration of study drug at Day 1.
- k. On Day 1, the eC-SSRS is to be administered prior to randomization. The eC-SSRS will be completed at the beginning of the visit following administration of other PROs required prior to injections. The eC-SSRS is not required during the Withdrawal visit if withdrawal occurs during the Extension Phase.
- l. Women of childbearing potential only. S=serum, U=urine. Pregnancy events will be captured starting at Day 1 following initial exposure to study drug. Serum pregnancy test can substitute for urine pregnancy test if locally required but must be appropriately timed to confirm pregnancy status prior to randomization and first IM administration. If the urine test is positive, perform a serum test and do not administer injection. The frequency of pregnancy tests should be performed according to local legal requirements.
- m. Month 12 (OLI and BIK) and Month 11 (D2I) HIV-1 RNA retest (within 4 weeks) for results > 50 c/mL will be captured as unscheduled visit. Plasma for storage samples will be used for possible future analyses.
- n. A morning specimen is preferred. To assess biomarkers: urine albumin/creatinine ratio; urine protein/creatinine ratio; urine phosphate; beta-2-microglobulin; and retinol binding protein.
- o. An overnight fast is preferred; however, a minimum of a 6-hour fast is acceptable.

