No.	Population	GSK Standard/ Example Shell	Title	Programming Notes	Deliverable [Priority]
3.46.	Safety	SAF_T9	Statistical Analysis of Log-Transformed Ratio to Baseline in HOMA-Insulin Resistance - MMRM	201584 primary_16/T6.08	M12
3.47.	Safety	SAF_T10	Statistical Analysis of Proportion of Subjects with HOMA-IR ≥ 2 , ≥ 3 and ≥ 4 at M12 (OLI and BIK) /M11(D2I) – Logistic Regression	See Section 8.5.4 for details. Note: Subjects with evidence of pre-study diabetes (via medical history or prior medications) are excluded.	M12
3.48.	Safety	SAF_T9	Statistical Analysis of Log-Transformed Ratio to Baseline in Bone Markers - MMRM	201584 primary_16/T6.08	M12
3.49.	Safety	SAF_T9	Statistical Analysis of Log-Transformed Ratio to Baseline in Renal Markers- MMRM	201584 primary_16/T6.08	M12
3.50.	Safety	SAF_T9	Statistical Analysis of Log-Transformed Ratio to Baseline in CCI - MMRM	201584 primary_16/T6.08	M12
3.51.	Safety	SAF_T8	Summary of Change from Baseline in CCI by Visit	Include baseline	M12
ECG					
3.52.	Safety	EG1	Summary of ECG Findings (Maintenance Phase)	207966/primary_15/T3.64	M12
3.53.	Safety	EG2	Summary of Change from Baseline in ECG Values by Visit (Maintenance Phase)		M12

Safety: Tables					
No.	Population	GSK Standard/ Example Shell	Title	Programming Notes	Deliverable [Priority]
3.54.	Safety	EG10	Summary of QTc Values by Category (Maintenance Phase)	207966/primary_15/T3.66	M12
3.55.	Safety	EG10	Summary of Change from Baseline QTc Values by Category (Maintenance Phase)	207966/primary_15/T3.67	M12
Vital Signs and Anthropometric Profile					
3.56.	Safety	VS1	By Phase Summary of Change from Baseline in Vital Signs by Visit	Q2M and BIK only	M6, M12, EOS
3.57.	Safety	SAF_T12	Summary of Shift in BMI Categories from Baseline by Visit (Overall and By Strata) – Maintenance Phase	Q2M and BIK only 207966/primary_15/T3.70 Month 5/6 and Month 11/12 For month 6 remove “ by visit” Only include Gender, as BMI is already one of the stratification factors (M12)	M6, M12
3.58.	Safety	SAF_T13	Summary of Change from Baseline in Weight and BMI by Gender, Baseline BMI, Race and by Visit (Maintenance Phase)	Q2M and BIK only 207966/primary_15/T3.71 Month 5/6 and Month 11/12 For month 6 remove “ by visit”. Do not need overall	M6, M12

Safety: Tables					
No.	Population	GSK Standard/ Example Shell	Title	Programming Notes	Deliverable [Priority]
3.59.	Safety	SAF_T14	Summary of Percent Change from Baseline in Weight (Maintenance Phase)	Q2M and BIK only	M6. M12

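### The D2I 2-hour post-dose ECG on Day 1 is classed by date alone as Screen / Pre-treatment, against the plan's own post-dose timepoint, and can be left out of Maintenance Phase ECG summaries

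*SAP*

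**What the plan says.** Section 16.4.1 states that "vital signs, and ECGs will be assigned to study phases as defined as in Section 16.4.1.2" and that "Assessments/events are assigned to study phases sequentially, starting from the top of each table". In 16.4.1.2 the Screen row is "Date ≤ Maintenance Treatment Start Date". The Maintenance row requires a strictly later date, and the date is the assessment date, with no clock time. Section 16.6.1 makes the treatment start date for the Q2M arm the date of the first dose, oral or injected; for D2I that is the first injection. Table 7 in 16.4.3 gives the pre-treatment state to "All assessments/events within Phase" for Screen.

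Footnote i of the schedule in Appendix 2, which limits post-dose tracings to those on the injectable regimen, provides: "A 2-hour post-dose ECG will also be performed at Day 1 (D2I), Month 1 (OLI) and Month 12 (OLI)/Month 11 (D2I").

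Other sections treat this ECG as a separate result. The D2I window table (16.3.2.2) has a post-dose ECG row, Day 1 (Post Dose), apart from Maintenance Baseline. Section 16.3.5 says which post-dose ECG to use when there are several. A note to the window table adds: "Analysis windows are applied after data has been assigned to the Maintenance Phase and Extension Phase as defined in Section 16.4.1". Section 5.2 sets the ECG baseline as "the mean of the last pre-treatment set of assessments from the same date", directly after saying that the Day 1 triplicate is taken before the first dose. Table 3.52 is titled "Summary of ECG Findings (Maintenance Phase"), and Tables 3.53 to 3.55 carry the same phase restriction.

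**The concern.** A tracing planned for two hours after an injection should not be coded as pre-treatment. The rule has no exception for it, so the label is wrong for every D2I participant who has this ECG. OLI participants are not affected, because their first-injection post-dose ECG comes about a month after treatment start.

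What is at stake is the QTc summary in the subgroup that starts injections with no oral run-in. QT prolongation is on the SAP's list of events of special interest for RPV, and the plan sets ECG values of potential clinical interest (QTc above 500 msec, or a rise of 60 msec or more). If the phase filter is applied as written, the category tables can describe the first-injection ECG for OLI and not for D2I. Two programmers following the same SAP could produce different D2I tables.

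**Working it through.** The plan gives no figure to reproduce. The check applies its date rules to the scheduled ECGs.

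**Step 1: classification.** Inputs: the phase rule in 16.4.1.2, the state rule in Table 7, the visits in Appendix 2, and the target study days in 16.3.2. Start date = Study Day 1. Screen if day ≤ 1; Maintenance if day > 1.

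| ECG | Study Day | Phase | State |
|---|---|---|---|
| Screening | before 1 | Screen | Pre-treatment |
| Day 1 pre-dose triplicate | 1 | Screen | Pre-treatment |
| D2I Day 1, 2 h post-dose | 1 | Screen | Pre-treatment |
| OLI Month 1 post-dose | target 31 | Maintenance | On-treatment |
| D2I Month 11 post-dose | target 331 | Maintenance | On-treatment |

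Only the third row is misclassified. Row order is not the cause, because the Maintenance row also excludes Day 1. The adverse event table (16.4.1.1) uses a strict inequality for Screen, so an adverse event starting on Day 1 is Maintenance while an ECG from the same day is Screen.

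**Step 2: how much D2I ECG information is involved.** Apart from a withdrawal visit, the scheduled on-drug D2I readings are Day 1 post-dose, Month 11 pre-dose and Month 11 post-dose. The affected tracing is 1 of 3, and the only one before Month 11 (target Day 331).

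**Step 3: which displays are exposed.** Table 3.53 is by visit, and the window table supplies a named row for this tracing. Tables 3.52, 3.54 and 3.55 have no by-visit wording in their titles, so a Maintenance or on-treatment filter could remove the value without leaving a visibly empty row. Listings 50 and 51 have no phase limit in their titles.

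**Step 4: baseline, as a conditional case only.** Assume one post-dose tracing and a true 2-hour change of D msec from the pre-dose mean. The values of D are illustrative and do not come from the SAP.

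- Pre-dose triplicate as baseline: reported change = D.
- Post-dose tracing averaged with the triplicate: baseline rises by D/4 and reported change = D − D/4 = 0.75 × D. For D = 60 this is 45 msec; a true change of 60/0.75 = 80 msec would be needed to show 60. Later changes shift by −D/4 (−2.5 msec for D = 10, −15 for D = 60).
- Post-dose tracing taken as the last recorded value: Day 1 change = 0, and later changes shift by −D.

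**The case against.** A reader might infer that this ECG disappears from every Maintenance Phase ECG table. The SAP does not establish that. Section 16.3.2.2 covers screening data as well as Maintenance and Extension data, and under 16.4.1.2 every Day 1 baseline record is itself Screen. If the note on windows barred Screen records, the baseline row would be empty and the change-from-baseline table could not be produced. Screen records must therefore be slotted, and the Day 1 (Post Dose) row can be filled. This stands for Table 3.53. It does not settle the tables that may pool Maintenance or on-treatment values.

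A reader might also infer that the tracing contaminates the QTc baseline. Section 5.2 sets a general pre-dose rule and places the triplicate before the first dose, so the set it means is most naturally that triplicate. Its fallback of assuming Day 1 assessments are pre-dose applies only when time is not collected. The ±30-minute allowance in footnote i and the closest-to-two-hours rule in 16.3.5 both presuppose that time is recorded. The contrary reading needs either the Table 7 meaning of pre-treatment, or a literal use of the baseline window, which runs by date up to and including the first dose. The wording leaves that open, but the better reading is against it.

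The safety consequence has limits too. A Day 1 QTc value of potential clinical importance can still appear in Listing 50, and an abnormal finding in Listing 51. The QT event of special interest is identified from adverse event terms, and adverse events starting on Day 1 count as Maintenance.

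**Conclusion.** The classification error is real and follows directly from stated rules: 16.4.1.2 and Table 7 conflict with 16.3.2.2 and 16.3.5 on the D2I Day 1 post-dose ECG, and OLI and D2I are handled differently at the first injection. It concerns one tracing per D2I participant, the only on-drug ECG scheduled before Month 11 apart from withdrawal.

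Omission from the summaries is possible rather than certain. It depends on the phase filter being applied literally, and is most likely in Tables 3.52, 3.54 and 3.55. The mock shells, which might show how these tables are laid out, are not in the document. Baseline contamination is a secondary ambiguity, and the D/4 shift holds only under the averaging assumption in Step 4. Efficacy and AESI reporting do not depend on this rule. It should be corrected, because it bears on how QTc is summarised after a first injection and is easy to put right.

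**What to change.** 1. In 16.4.1.2 and Table 7, add an exception: an ECG recorded after the first dose on the Maintenance Treatment Start Date (by clock time or post-dose flag) is Maintenance / On-treatment.
2. In 5.2 and 16.3.2, state that the ECG baseline uses pre-dose tracings only.
3. Confirm in 16.15.7 that Day 1 (Post Dose) feeds Tables 3.52 to 3.55 for D2I.
4. Reconcile the Day 1 (Post Dose) rows in both the OLI (16.3.2.1) and BIK (16.3.2.3) window tables with footnote i, which schedules no Day 1 post-dose ECG for either group.

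The cost is SAP wording and one derivation rule. The ECG is already scheduled, so no new data are needed.
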